3.1.2. SECONDARY STUDY OUTCOMES

- Relative change in clinical threshold (No observed adverse event level, NOAEL; Lowest observed adverse event level, LOAEL) to roasted peanut at 6 and 12 months.
- Rate of sustained unresponsiveness after 4 week cessation of maintenance OIT at 1 year and 3 years.
- Change in quality of life (QoL) assessments at 6 and 12 months after OIT, as assessed by FAQL-Questionnaire in children, teenagers and their parents in the active vs control group.
- Safety of OIT using boiled peanut as defined by frequency and nature of allergic symptoms experienced.
- Compliance with study protocol
- Immunological outcome measures pre-, during and post-OIT

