- **Contact information** for the team, which will includes a dedicated mobile phone number with 24/7 access to a senior member of the medical team for urgent queries, and an email address which will be checked daily by the research team from Monday to Friday for non-urgent queries.
- **Dietary advice on peanut avoidance**. Participants receiving OIT will not be allowed to ingest peanut for the whole study duration (52 weeks) excluding the OIT doses.
- A home diary and instruction sheet, which will specify to parents what dose to give their child, and on to which they will log all doses taken at home and any resulting adverse events. Subjects will be asked to record any symptoms, duration, timing in relation to OIT dose and any exacerbating factors (e.g. exercise, excessive tiredness, viral illness). In the event of any symptoms, the family needs to contact the research team for advice. Participants will also be offered an opportunity to 'opt-in' to using an electronic 'mobile app' diary in parallel to the paper-based diary, the aim being to facilitate reporting by study participants and validate this approach for future OIT studies.

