7. STATISTICS AND DATA ANALYSIS

7.1 SAMPLE SIZE ESTIMATION

Current data from Europe and North America indicates that at least 80-85% of peanut-allergic children will react to 1.4g peanut protein. The incidence of natural resolution of peanut allergy over a 12 month period is typically <10%, on the basis of data arising from our clinical service.

For the purpose of this study, we have assumed a conservative estimate of 10% for natural resolution, and a 20% dropout rate. We note that such is the demand for OIT that in the published studies, drop-out rates have been consistently <10%.

We propose to recruit 46 peanut-allergic children to the study, who will be randomized 2:1 to active (n=30) or control (n=16) groups. This will allow us to detect a rate of successful desensitisation of 60% in participants undergoing OIT, with 80% power using a two-sided significance level of 0.05 and with continuity correction, whilst allowing for a 20% loss-to-follow-up.

These figures for desensitisation rate and resolution are based on published data relating to the UK.⁷

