7.2.2 ANALYSIS OF SECONDARY ENDPOINTS

The following secondary analyses will be performed, using two-sided testing for non-parametric data at a p<0.05 level of significance:

- Relative change in clinical threshold (NOAEL, LOAEL) to roasted peanut at 6 and 12 months in active vs control, using Mann-Whitney U test.
- Proportion of subjects who tolerate 1.4g (or more) roasted peanut protein in the active and control groups, 12 months after randomization and following cessation of all peanut intake for 4 weeks after 1 and 3 years of OIT, using a two-sided Fisher's exact test at a p<0.05 level of significance.
- Change in quality of life assessments before, and at 6 and 12 months after OIT, as assessed by FAQL-Questionnaire in children, teenagers and their parents in the active vs control groups using paired and group comparisons by non-parametric testing.
- The incidence of adverse events experienced between active and control groups. Statistical differences will be
 determined using Fisher's exact test for proportions or using non-parametric tests for graded reactions.
 Logistic regression will be used to assess the influence of age, gender, asthma status and prior history of
 anaphylaxis on incidence of adverse events.
- Immunological outcome measures pre-, during and post- 12 months of OIT, using Mann-Whitney U test (for paired comparisons) or Friedman's test (for trends over time).

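### Safety is defined partly by how often allergic symptoms occur, but section 7.2.2 plans no analysis of frequency, and its four-covariate logistic model is too large for about 30 treated children

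*Combined protocol and SAP*

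**What the plan says.** Section 3.1.2 lists as a secondary outcome: "Safety of OIT using boiled peanut as defined by frequency and nature of allergic symptoms experienced". That has two parts, how often symptoms occur and what they are like.

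Section 7.2.2 gives the matching analysis. The quantity is "The incidence of adverse events experienced between active and control groups", tested by Fisher's "exact test for proportions or using non-parametric tests for graded reactions". It adds: "Logistic regression will be used to assess the influence of age, gender, asthma status and prior history of" anaphylaxis on adverse event incidence.

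The section does not say whether the unit is a child, a reaction or a dose, or which event or grade makes a case. It does not say whether the logistic model covers the treated children or all 46, whether it includes arm, or what is done if it cannot be fitted.

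On data collection, section 5.3.4 has active-arm families keep a diary in which "they will log all doses taken at home and any resulting adverse events". Under 5.3.4.1 each dose increase is first given on the Research Unit. Control families log accidental reactions (5.3.3).

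**The concern.** The study hypothesis (1.2) includes an acceptable safety profile, safety is the first secondary objective (2.2), and the case for boiled peanut in 1.1 is that it may be safer and better tolerated. How often a treated child reacts is therefore a main result for families and clinicians.

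None of the planned methods estimates it. Fisher's test and logistic regression reduce each unit to yes or no, and the test on graded reactions addresses severity. Applied per child, they ignore the difference between one reaction a year and thirty. Applied per reaction or per dose, they treat repeated events in one child as independent, which neither method allows.

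The risk-factor model has its own problem. Four covariates in about 30 treated children is heavy for any binary outcome. If nearly all or very few children have an event, maximum likelihood may have no finite solution, and 7.2.2 names no fallback.

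**Working it through.** **The plan's own figure.** The documents state no figure for the safety analysis. The only calculation to reproduce is the sample size in 7.1: "randomized 2:1 to active (n=30) or control (n=16) groups". Its inputs are success in 60% on OIT against 10% in controls, power 80%, two-sided level 5%, a continuity correction and 20% loss. For ratio k = 2 the pooled proportion is (0.10 + 2 × 0.60)/3 = 0.433, and the control-arm size is

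[1.96 × √(0.433 × 0.567 × 1.5) + 0.842 × √(0.09 + 0.24/2)]² / 0.50² = 9.92.

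The continuity correction gives (9.92/4) × [1 + √(1 + 3/(9.92 × 0.50))]² = 12.75. The total is 3 × 12.75 = 38.2, and 38.2/0.8 = 47.8. At the actual ratio 30/16 the total is 46.9. The stated 46 is reproduced within two children, and this point does not affect it.

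**What a per-child proportion retains.** Dosing is daily (5.3.4) for 52 weeks (section 3), so at most 52 × 7 = 364 doses. Missed doses and withdrawals reduce this. The documents give no reaction rate, so the per-dose risk q is assumed. With independent doses and equal risk, P(any reaction) = 1 − (1 − q)^364.

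| Assumed q | Expected reactions per child-year (364q) | Children with any reaction |
|---|---|---|
| 0.1% | 0.36 | 31% |
| 0.25% | 0.91 | 60% |
| 0.5% | 1.8 | 84% |
| 1% | 3.6 | 97% |
| 2% | 7.3 | 99.9% |
| 5% | 18 | about 100% |

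Between 1% and 5% per dose, reactions rise fivefold while the expected number of affected children out of 30 moves from 29.2 to 30.0. Between 0.1% and 0.5%, also fivefold, the proportion moves from 31% to 84%.

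Children will differ in risk. With a negative binomial count (mean m per year, shape k), P(any) = 1 − [k/(k + m)]^k. At k = 1, m = 5 gives 83.3% and m = 40 gives 97.6%: eight times the reactions for 14 points. At k = 0.5 the same means give 70% and 89%.

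**The logistic model.** In 30 children the smaller outcome class per covariate is 30 × 0.5/4 = 3.75 at 50% incidence, 30 × 0.2/4 = 1.5 at 80% and 30 × 0.1/4 = 0.75 at 90%.

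The chance of no finite estimate was simulated (1,500 data sets per cell, linear-programming check for complete or quasi-complete separation). Assumed: age uniform 8 to 16, half male, half with asthma, 40% with prior anaphylaxis, no true effects.

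| Incidence | 30 children | 24 children (20% lost) |
|---|---|---|
| 5% | 88% | not run |
| 10% | 62% | not run |
| 20% | 20% | not run |
| 30% | 5% | 13% |
| 50% | 1% | 2% |
| 70% | 5% | 13% |
| 80% | 19% | 33% |
| 90% | 64% | 74% |
| 95% | 86% | 92% |

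With an odds ratio of 2 for each binary factor, the 30-child figures are 11% at 70%, 35% at 80% and 72% at 90%. If only 20% have prior anaphylaxis and there are no true effects, they are 9% at 50%, 38% at 80% and 73% at 90%.

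For all 46 children without an arm term, separation is about 0.1% or less when incidence differs by arm (50–95% active, 10–20% control). When incidence is equal in both arms it is 0–6% at 30–80% incidence, 36% at 90% and 74% at 95%. When incidence differs by arm and an arm term is added, it is 7–63%.

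**The case against.** The planned comparison is active against control, and for that question a per-child Fisher test can work well: an illustrative 24 of 30 against 3 of 16 gives p of about 0.0001. This stands. A per-dose rate has no value for controls in the first year, so it cannot replace the randomised comparison. It also stands that the graded test covers the severity half of the outcome, and that the current wording already permits Fisher's test on serious reactions.

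A reader might infer that the plan specifies a per-child test. It does not: the unit is left open, and per child is only the reading under which the methods are valid.

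A reader might also infer that the planned analysis can never separate a well-tolerated regimen from one with five times the reactions. The documents do not support that. Saturation depends on a per-dose risk they do not give, and section 1.1 describes pilot symptoms at updosing as minimal, so low rates cannot be ruled out.

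Nor do the documents show that the logistic model will usually fail. Failure is uncommon at mid-range incidence and close to nil for all 46 children without an arm term when the arms differ. That last version has a different weakness: it mixes dosed children with children avoiding peanut, so it cannot show who reacts to OIT.

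Finally, the diary alone does not hold every dose. It covers home doses, and the first dose of each step is given in hospital.

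**Conclusion.** The concern holds in a limited form. The frequency half of the safety outcome has no planned analysis, and the unit of the planned tests is undefined. Neither conclusion depends on an assumed rate.

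How much a per-child proportion loses does depend on one. It is close to 100% at about 1% per dose or more with independent, equal risks; it is not saturated at 0.1% to 0.5%; and it saturates more slowly if children differ in risk.

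The four-covariate model is overfitted for about 30 treated children at any incidence, with at most 3.75 children in the smaller class per covariate. Outright failure is a risk only towards the extremes: about 20% at 20% or 80% incidence and over 60% at 10% or 90%, under the assumed covariate mix.

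This is a secondary outcome. The primary analysis and the sample size are unaffected.

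**What to change.** In 7.2.2:

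- State that Fisher's test compares, between arms, the number of children with at least one reaction, with a serious reaction, and with adrenaline use. Define a serious reaction so that a control child can also meet it, because the anaphylaxis-treatment rule in 6.1 is tied to an OIT dose.
- State that graded reactions are compared by the highest grade per child.
- Add, for OIT-treated children (active arm, plus controls who cross over in WP2), reactions per 100 OIT doses with a confidence interval clustered by child. Count doses from the home diary and the Research Unit records together.
- Assess age, sex, asthma and prior anaphylaxis in those children with a negative binomial model on reaction counts, with log(doses taken) as offset. Label it exploratory.
- Use Firth-penalised logistic regression for any binary outcome that is kept.

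Section 5.5 gives crossover controls an identical protocol, so up to 30 + 16 = 46 children could contribute if all take it up and none are lost.

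The cost is SAP wording, some programming and the linking of hospital doses to diary doses; no new assessments are needed. Four covariates remain imprecise at this size under any model. The per-dose rate supplements the between-arm comparison and does not replace it.

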5.5 WP2: YEAR 2 OF STUDY

Children in the control group will be offered OIT using boiled PN during months 12-24. An identical protocol to WP1 will be used (section 5.3.3).

Children in the active group (who underwent OIT during months 1-12) will be offered ongoing maintenance therapy, as described above in section 5.4.

5.6 2 YEAR ASSESSMENT

Children who were originally assigned to the control group and who have undertaken OIT during months 12-24 will undergo a further DBPCFC to roasted PN at 24 months. The DBPCFC will be performed as in Section 5.2.2. The purpose of this challenge is to assess for the development of sustained unresponsiveness to roasted peanut following OIT, and the resulting change in threshold of clinical reactivity.

All subjects will also undergo repeat skin prick testing to commercial crude peanut extract and boiled peanut slurry, and quality-of-life assessments as described in section 5.7.1.

All children (in both control and active groups), apart from those who passed the tolerance challenge at 13 months, will be offered a further tolerance challenge at 24 months, to be performed as in section 5.4.

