It is therefore important for this study to include mechanistic assessments to allow for markers of successful desensitisation to be assessed, in order to improve the efficacy of future OIT protocols. We will include a series of laboratory assessments in subjects undergoing OIT, allowing longitudinal comparisons to be made in those undergoing OIT (vs controls) to assess the following:

- Changes in serum specific antibodies pre- and post-OIT: Total IgE; specific IgE, IgG4 to whole peanut and peanut components (Ara h 1, 2, 3, 8 and 9) and their ability to cause an effector cell response will be measured
- IgE-immunoblot using patient sera to identify in vitro the binding of participants IgE to peanut proteins, and how this varies during OIT.
- Identification of serum factors associated with the development of oral tolerance during peanut OIT, by means of a validated IgE facilitated-binding assay.
- Changes in basophil responses (assessed by CD63 and CD203c expression by flow cytometry) following *in vivo* and *ex vivo* peanut stimulation, and how these vary during OIT. Confirmatory work will be performed in a subset of patients using purified basophils isolated from whole blood.
- Biomarkers that may identify successful tolerance induction to peanut
- Changes in T and B cell populations and their immune profile during OIT, including allergen-specific proliferation of T-cell subtypes (including T helper and regulatory T cells) and changes in immunoglobulin repertoire by peanut-specific B-cells.
- mRNA expression and methylation of proteins (such as forkhead box protein 3 (FOXP3) sites) on T cell subsets which may predict the presence of sustained unresponsiveness.

These assessments will be performed on blood samples taken at baseline, 3, 6, 12, 13 and 24 months, as well as at the 3 year assessments (outlined in Figure 8) after commencement of OIT. Laboratory work will be initially performed at the National Heart & Lung Institute, Imperial College London, although some assays may be performed elsewhere in the UK or abroad, where lack of local expertise necessitates this). Specimens may also be stored for future use in new assays to measure immune responses or biomarkers, as research tests are developed.

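### Section 7.2.2 assigns the Mann-Whitney U test, which assumes independent samples, to paired within-child immunology comparisons; with positively correlated repeat values it is conservative and loses power for modest changes

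*Combined protocol and SAP*

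**What the plan says.** Section 3.1.2 lists as a secondary outcome "Immunological outcome measures pre-, during and post-OIT". Section 7.2.2 gives the analysis: "Immunological outcome measures pre-, during and post- 12 months of OIT, using Mann-Whitney U test (for paired comparisons", with "Friedman's test (for trends over time" as the alternative. The lead-in to that list sets the error rate: "using two-sided testing for non-parametric data at a p<0.05 level of significance".

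Section 5.8.3 describes the data. Blood is taken from the same children at baseline, 3, 6, 12, 13 and 24 months and at the 3-year assessments. The first item to be assessed is "Changes in serum specific antibodies pre- and post-OIT", and the stated purpose of the series is "allowing longitudinal comparisons to be made in those undergoing OIT (vs controls".

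No paired two-sample rank test is named anywhere in the plan. No power, correlation or effect size is given for any immune marker.

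**The concern.** A comparison of before and after values in the same child is paired. The Mann-Whitney U test treats the two sets of values as if they came from different children. Its null variance therefore leaves out the covariance between a child's two values. If that covariance is positive, the variance used is too large, the true error rate falls below 5%, and power is lost.

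The bullet also leaves a gap. It names no arms and no active-versus-control test for immunology, although section 5.8.3 says that the longitudinal comparison is made against controls.

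At stake is the ability to detect modest immune changes in a small treated group. There is also a practical cost: at analysis the team must either run a test that does not fit the design or depart from the plan after the data are in.

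**Working it through.** **1. Does the text mean paired data?** Four points say yes.

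- The bullet lists time points (before, during, after), not arms.
- Friedman's test, offered in the same sentence, is a related-samples test.
- The quality-of-life bullet in the same list reads "in the active vs control groups using paired and group comparisons by non-parametric testing", so the authors treat paired and group comparisons as different things.
- Section 5.8.3 describes serial samples from each child.

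**2. Inputs.** From section 7.1: 30 active, 16 control, 20% loss. Pairs: 30 × 0.8 = 24. Controls: 16 × 0.8 = 12.8, taken as 13. From section 7.2.2: two-sided 5%. Assumed, because the plan gives neither: within-child correlation ρ from 0 to 0.7, and a change of 0 to 1.0 SD.

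**3. The plan's own figure.** The only stated size is 46, for the primary endpoint. With 10% v 60%, 2:1 allocation, 80% power and pooled proportion (0.1 + 2 × 0.6)/3 = 0.433:

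- n = [1.96√(0.433 × 0.567 × 1.5) + 0.842√(0.09 + 0.24/2)]² / 0.5² = 9.92 controls
- with continuity correction, (9.92/4)[1 + √(1 + 2 × 1.5/(9.92 × 0.5))]² = 12.75 controls
- total 3 × 12.75 = 38.2 evaluable; 38.2/0.8 = 47.8

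That is within 2 of 46. There is no corresponding figure for immunology to reproduce.

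**4. Why pairing matters.** The SD of a within-child difference is √(2(1 − ρ)) SD: 1.41, 1.18, 1.00 and 0.77 at ρ = 0, 0.3, 0.5 and 0.7. A 0.5 SD change is therefore 0.35, 0.42, 0.50 and 0.65 SDs of the difference. The signed-rank test uses this gain; Mann-Whitney does not.

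**5. True error rate of Mann-Whitney on paired data.** Large-sample formula: 2[1 − Φ(1.96/√(1 − ρs))], with ρs = (6/π)arcsin(ρ/2). Simulation: bivariate normal, equal variances, 24 pairs, 10,000 data sets per setting (Monte Carlo SE at most 0.5 points).

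| ρ | Formula | Simulated |
|---|---|---|
| 0 | 5.0% | 4.6% |
| 0.3 | 2.0% | 2.1% |
| 0.5 | 0.6% | 0.8% |
| 0.7 | 0.05% | 0.1% |

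The signed-rank test stays at 4.7–5.0%.

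**6. Power, Mann-Whitney v signed-rank, 24 pairs.**

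| Change | ρ = 0 | ρ = 0.3 | ρ = 0.5 | ρ = 0.7 |
|---|---|---|---|---|
| 0.5 SD | 36% v 36% | 34% v 49% | 34% v 63% | 31% v 84% |
| 0.75 SD | – | 73% v 83% | 76% v 93% | 81% v 99% |
| 1.0 SD | – | 94% v 97% | 96% v 99.5% | 99% v 100% |

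With all 30 pairs and 0.5 SD: 45% v 59%, 43% v 74% and 44% v 92% at ρ = 0.3, 0.5 and 0.7.

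**7. Change needed for 80% power, 24 pairs** (0.05 SD grid): 0.80 SD with Mann-Whitney against 0.65 SD with signed-rank at ρ = 0.5, and 0.75 against 0.50 SD at ρ = 0.7.

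**8. Active v control, 24 v 13, difference 0.5 SD.** Mann-Whitney on change from baseline v on follow-up values: 20% v 26% at ρ = 0.3, 27% v 27% at 0.5, 42% v 27% at 0.7.

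**The case against.** The strongest reply is that this is a naming slip. The word paired, and Friedman's test beside it, show that the authors had related samples in mind. A statistician following the plan would probably notice and use the paired test, in which case no power is lost. That lowers the practical risk, but the sentence still needs correcting. If the slip was instead in the word paired, and active v control was meant, then no within-child two-time-point test is specified at all.

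The size rests on assumptions. The plan does not say whether the immune changes are modest or large, and the result runs from no loss to 53 points (84% − 31%) across the range shown. The normal model also favours the signed-rank test, which depends on the measurement scale as Mann-Whitney does not. With log-normal values tested untransformed (log-SD 1 to 1.5, also assumed), signed-rank power for the 0.5 SD change falls from 63% to 53–56% at correlation 0.5, and from 84% to 73–77% at 0.7. The gap narrows but remains substantial.

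Conservative also means positive correlation. At −0.3 the Mann-Whitney error rate rises to about 8%. Negative correlation is unlikely for repeat values in one child.

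Finally, using change from baseline between arms is a choice. By step 8 of the working it costs power at correlation 0.3 and gains only above 0.5.

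**Conclusion.** The concern holds. As written, the plan pairs the data and names a test for unpaired data. Under positive within-child correlation the result is a conservative test, not false positives. For a 0.5 SD change in 24 children the loss is about 15 points of power at correlation 0.3, 29 at 0.5 and 53 at 0.7. For a 1 SD change it is at most about 4 points. These sizes rest on assumed correlations and effect sizes, normal data and equal variances. The direction needs only a positive correlation.

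The consequence is limited to one mechanistic secondary outcome. It should be corrected, but it does not touch the primary analysis or the sample size.

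**What to change.** Replace the test wording in the immunology bullet of section 7.2.2 with: *within-child comparisons by Wilcoxon signed-rank test; active v control by Mann-Whitney U test on change from baseline.* Change from baseline fits section 5.8.3, which asks about changes, and the threshold bullet in 7.2.2, which already compares relative change between arms. Since signed-rank results depend on scale, it would help to state the scale or transformation for each marker.

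Also state whether controls treated in year 2 contribute to the within-child comparison. Section 5.5 says of them "An identical protocol to WP1 will be used", but the analysis plan is silent. If all did, there would be at most 24 + 13 = 37 pairs, and power for a 0.5 SD change would be 56% v 82% at correlation 0.5 and 59% v 96% at 0.7 (Mann-Whitney v signed-rank).

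Optional: Friedman's test is valid for repeated measures but ignores the order of visits; Page's test would suit a trend over time better.

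The cost is one sentence for the tests, plus a line on the year-2 controls. The data, samples and standard software stay the same.

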5.4.2 TOLERANCE CHALLENGE AT 13 MONTHS

Children in the active group who meet the primary study outcome (desensitised to >1.4g peanut protein at DBPCFC) will then be instructed to stop all peanut exposure (including OIT doses). A further open challenge will be performed after 4 weeks, according to protocol 3, using criteria listed in Section 5.2.2 to determine outcome. Children who tolerate at least 1.4g peanut protein at this challenge will continue with thrice weekly maintenance peanut therapy (4-8 peanuts). Those who react will recommence updosing to the previously tolerated dose and then continue daily maintenance peanut until the 24 months time point.

Protocol 3: Open OFC to roasted PN	Roasted peanut OFC (using defatted flour)		OUTCOME if reacts	
TIME POINT (mins)	Peanut flour	Peanut protein		
0	20	10	RECOMMENCE OIT and updose to previous tolerated dose. Then continue DAILY maintenance of up to 4 peanuts. Repeat tolerance OFC at 24 mths Change to minimum thrice weekly maintenance dose of 4 peanuts.	
30	60	30		
60	200	100		
90	600	300		
120	2000	1000		
150	6000	3000		
Cumulative dose		4440mg	If no reaction:	
2 hour observation period following last dose			Change to thrice weekly maintenance dose of 4-8 peanuts	

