5.8.2 QUALITY OF LIFE ASSESSMENTS

The impact of OIT on participants' quality of life (QoL) will be assessed both from parents' and participants' perspective using abbreviated versions of disease-specific validated "food-allergy quality of life questionnaire" (FAQL-Q) in its parental, ¹⁴ child¹⁵ and teenage¹⁶ forms at baseline, 3, 6, 12, 24 and 36 months in both the active and control groups. These new abbreviated versions have been validated (data submitted for publication). We will also assess the impact of the child's food allergy on parent QoL, using the FAQL-Parent Burden form (which has been validated in a UK population).¹⁷ QoL assessments will be done both prior to and after oral challenges.

The FAQL-questionnaires are based on a 7-point Likert scale and changes greater than 0.5 points over time have been defined as clinically significant. Previous studies have reported a positive effect on QoL following OIT to peanut from the parents' perspective, however, there are no controlled studies which have addressed the impact on QoL as perceived by participants. This is a significant knowledge gap, since there is a concern that while parents report an improved QoL when their child undergoes OIT, the child themselves may experience a worsening of QoL due to frequent side effects and need to alter their activities following OIT doses.

In line with current expert opinion, and to ensure the ability to compare responses consistently during the first 12 months of OIT, children who are age 12 at study commencement will be asked to complete the Teenage versions of the QoL assessments, unless there are difficulties with comprehension which preclude this.

We will also assess parental anxiety before, and 12 and 24 months after their child commencing OIT, using the Perceived Stress Scale.¹⁹

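### The immunology analysis in 7.2.2 names no control arm, although 5.8.3 promises that comparison, and it assigns an unpaired test to paired data

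*Combined protocol and SAP*

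**What the plan says.** Section 3.1.2 lists "Immunological outcome measures pre-, during and post-OIT" as a secondary outcome and names no comparator. The matching bullet in 7.2.2 covers "Immunological outcome measures pre-, during and post- 12 months of OIT" and gives the methods as "using Mann-Whitney U test (for paired comparisons) or Friedman's test (for trends over time"). It mentions no control group.

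The other four bullets in 7.2.2 (threshold, tolerance of 1.4 g, quality of life, adverse events) all name the active and control groups. The first reads "Relative change in clinical threshold (NOAEL, LOAEL) to roasted peanut at 6 and 12 months in active vs control, using Mann-Whitney U test".

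Section 5.8.3 describes the laboratory programme as "allowing longitudinal comparisons to be made in those undergoing OIT (vs controls) to assess the following". It then states: "These assessments will be performed on blood samples taken at baseline, 3, 6, 12, 13 and 24 months", plus the 3-year assessments, all counted from the start of OIT. Section 5.3.3, on the control group, lists no blood samples. Section 5.2.3 provides for blood at the baseline challenge, which every child has before randomisation. Section 5.4 invites both arms to a 12-month challenge and repeats skin prick testing in all subjects at that assessment.

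**The concern.** For 12 months the trial has a randomised untreated arm, and section 3.2 says it is there to control for natural resolution. If the immunology analysis ignores that arm, any change over the year from ageing, natural course, the peanut eaten at the baseline challenge or assay drift is credited to OIT. Mechanistic claims would then rest on uncontrolled change.

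The second problem is the test. Mann-Whitney U assumes two independent samples. A child's value before OIT and the same child's value during or after OIT are correlated, and the test discards that correlation. Either the test or its label is wrong, so an analyst could not tell from the bullet which contrast was meant.

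**Working it through.** **Plan's own figure.** The documents give no sample size, power or effect size for immunology. The total of 46 in 7.1 concerns the primary endpoint. From it I take the arm sizes, 30 and 16, and the 20% loss: 30 × 0.8 = 24, and 16 × 0.8 = 12.8, taken as 13.

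**Step 1: the text.** Four of the five bullets in 7.2.2 name both groups. The immunology bullet does not, while 5.8.3 says the comparison is with controls. The two sections do not match.

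**Step 2: what a within-OIT test picks up.** Simulation, 3,000 runs per setting, 24 active and 13 control children, four visits. The model is value = √ρ·u + √(1−ρ)·e + slope·t, with u and e standard normal, t rising evenly from 0 to 1 over the four visits, and the same slope in both arms, so OIT has no effect. The slope, the correlation ρ and normality are assumptions, not figures from the documents.

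| Shared trend | ρ | Friedman within OIT, p<0.05 | Mann-Whitney on change, active v control, p<0.05 |
|---|---|---|---|
| 0.3 SD | 0.5 | 17% | 5% |
| 0.3 SD | 0.8 | 36% | 5% |
| 0.5 SD | 0.5 | 41% | 5% |
| 0.5 SD | 0.8 | 84% | 5% |

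Friedman is doing its job here, because there is a real trend. But the trend is not due to OIT, and only the between-arm test shows that.

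**Step 3: Mann-Whitney on paired values.** The test takes the variance of the mean difference as about 2σ²/n, while for pairs it is 2σ²(1−ρ)/n. The effective critical value is therefore about 1.96/√(1−ρ).

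- ρ = 0.5: 1.96/√0.5 = 2.77, two-sided size about 0.6%.
- ρ = 0.8: 1.96/√0.2 = 4.38, two-sided size about 0.001%.

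The simulation agrees: 0.6% and 0.0% for Mann-Whitney, against 5.0% and 4.7% for signed-rank. For a true 0.5 SD change in 24 children:

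| ρ | Mann-Whitney, misused | Wilcoxon signed-rank |
|---|---|---|
| 0.5 | 33% | 63% |
| 0.8 | 29% | 94% |

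**Step 4: Friedman and missing samples.** Friedman needs every visit in every child. If the 3, 6 and 12-month samples were each missed independently with probability m (an assumption), complete sets among 24 children would be 24 × (1−m)³: 20.6 at m = 5%, 17.5 at 10% and 12.3 at 20%.

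**Step 5: what the between-arm comparison can detect.** At 80% power and two-sided 0.05, the detectable difference is (1.960 + 0.842) × √(1/n₁ + 1/n₂), divided by √0.955 for Mann-Whitney, in SD units of the change score.

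- 24 v 13: 2.802 × 0.344 = 0.965; 0.965/0.977 = 0.99.
- 30 v 16: 2.802 × 0.310 = 0.867; 0.867/0.977 = 0.89.

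The SD of the change is √(2(1−ρ)) times the marker's own SD. So 0.99 corresponds to 0.99 marker SD at ρ = 0.5 (√1 = 1) and to 0.99 × 0.632 = 0.62 marker SD at ρ = 0.8.

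**The case against.** The best defence is that a between-arm comparison was intended. Mann-Whitney U is a two-group test, the threshold bullet in the same list uses it for active versus control, and 5.8.3 mentions controls. On that view only the word for pairing is a slip. This stands to the extent that the bullet is ambiguous: that the analysis is confined to OIT children is the natural reading, not a statement in the text. It does not rescue the bullet, since on either reading the contrast must be stated and the test or its label corrected.

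It is also fair that immunology is one secondary outcome among several, that the primary analysis is untouched, and that some laboratory aims, such as markers of successful tolerance, concern differences among treated children, where controls add little.

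Three stronger readings are tempting, and the documents do not support them.

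- A reader might infer a complete-case rule under which OIT failures leave the analysis. Complete blocks are a property of Friedman's test, and the plan contains no such rule. Under 5.3.4.2, children who fail the transition to roasted peanut stay on boiled peanut until the 1-year assessment. Under 5.4.1, withdrawal for an unsuccessful result follows the 12-month challenge. Only children withdrawn from treatment earlier lack stated further blood samples (4.3 and 7.2 keep them for quality of life).
- A reader might infer that the series contains responders only, at most 30 × 0.6 = 18 of 30. That needs month 13 to enter the series, and the 12-month sample can satisfy the bullet. Section 5.4.2 addresses the month-13 challenge to "Children in the active group who meet the primary study outcome", but sections 3 and 5 describe the active group without that limit, and 5.8.3 does not expressly restrict month-13 blood.
- A reader might extend the point to the Perceived Stress Scale, timed "12 and 24 months after their child commencing OIT". The same sentence also provides a measurement beforehand, and the scale is listed neither in 3.1.2 nor in 7.2.2. The absence of a baseline for control parents is an inference and a separate matter.

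**Conclusion.** The point holds for the missing comparison and the mislabelled test. Sections 7.2.2 and 5.8.3 disagree on whether controls enter the immunology analysis, and as written 7.2.2 yields tests whose results cannot be attributed to OIT. With a shared trend of 0.3 to 0.5 SD and no OIT effect, a within-OIT Friedman test is significant in 17% to 84% of simulated trials, while the between-arm test stays at about 5%. Mann-Whitney on paired values has a size below 1% and roughly 30% power for a 0.5 SD change, where signed-rank has 63% to 94%. These figures rest on assumed trends, correlations of 0.5 to 0.8, normal data and 24 versus 13 evaluable children. The mismatch between the sections and the error in the test label rest on the text alone.

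**What to change.** In 7.2.2, make the main immunology analysis the active versus control difference in change from baseline to month 12. Use ANCOVA on suitably transformed values adjusted for baseline, or Mann-Whitney on the change, and report estimates with confidence intervals. Limit the randomised contrast to months 0 to 12, because controls are offered OIT afterwards.

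For data, use skin prick tests, which both arms have at month 12, and blood taken at the 12-month challenge. Take that blood from all controls who attend, since using only those entering WP2 would select the comparator by willingness to start OIT. Confirm in 5.8.3 that controls are sampled then, and state whether they are sampled at 3 and 6 months. Without those samples a full arm-by-visit model may not be estimable.

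Within OIT children, use the Wilcoxon signed-rank test for pairs and, in place of Friedman, a mixed model on all available samples for trends. Report 13-month values descriptively, because under 5.4 and 5.4.2 that challenge is for children who met the month-12 threshold.

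The cost is rewording and slightly more analysis, plus a control sample at a visit already planned if none is currently taken there. The limitation is power: about 1 SD of the change score is the smallest difference detectable at 80%, so intervals should carry the interpretation.
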